6 STATISTICAL CONSIDERATIONS

6.1 Study Design

This is a single-center, open-label, randomized controlled trial. Study objective is To evaluate the safety and efficacy of intramyocardial injection of Allogenic Human Induced Pluripotent Stem Cells-derived Cardiomyocytes in patients with severe chronic ischemic heart failure with coronary artery bypass grafting indications. The sample size for this study is 20.

6.2 Study Duration

Patient enrollment is projected to require 6 months. All subjects will continue protocol-mandated follow-up through the 12-month (12M) visit as scheduled.

6.3 Sample Size Determination

This is an exploratory study. The total sample size is 20, with 10 allocated to the cell therapy group and 10 to the control group

6.4 Randomization and blinding

The trial employed an open-label design with single-blind outcome assessment. To mitigate evaluation bias, Assessors assessing treatment efficacy were blinded to group assignments.

Prior to trial initiation, a statistician generated 20 randomization codes using SAS PLAN procedure with 1:1 allocation. Sequentially numbered (1-20), opaque sealed envelopes containing group assignments were prepared, each bearing its corresponding identification number. Following written informed consent and successful screening, the designated envelope was opened immediately before surgery to reveal group allocation and initiate the assigned procedure. This ensured allocation concealment during screening and prerandomization phases, preventing selection bias.

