PRA	Population reactive antibody
DSA	Anti-donor specific antibodies
CEA	Carcinoembryonic antigen
CA125	Glycogen 125

AFP	Alpha-fetoprotein
ADR	Adverse reactions
AE	Adverse events
SAE	Serious adverse events
CRF	Case report form
DSMB	Data and Safety Monitoring Board
EC	Ethics Committee
GCP	Good Clinical Practice
CI	confidence interval
ICF	Informed Consent Form
HIV	Human immunodeficiency virus
HCV	Hepatitis C virus
HBV	Hepatitis B virus
TP	Treponema Pallidum

Protocol (version 6.1)

Version data: 2021.08.01

Confidential
Page 10 of 38

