3 STUDY DESIGN

This is a single-center, open-label, randomized controlled trial involving 20 eligible subjects who meet the inclusion/exclusion criteria. Subjects will be randomly allocated in a 1:1 ratio into two groups:

- Control Group: Standard CABG treatment only
- Cell Therapy Group: CABG + cellular transplantation (dose: 2 × 10⁸ cells) + perioperative immunosuppressive therapy

Postoperative Management:

All patients will undergo rigorous perioperative monitoring (within the first postoperative month) with comprehensive contingency protocols in place.

Follow-Up & Assessments:

Both groups will undergo identical follow-up evaluations at 1, 6, and 12 months, including:

Protocol (version 6.1)

Version data: 2021.08.01

Confidential
Page 17 of 38

Imaging studies (as per protocol), Laboratory investigations, Functional assessments. Documentation will be maintained via case report forms (CRFs) to ensure accurate and reliable data acquisition.

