4 STUDY TREATMENT

4.1 Treatment and dosage

4.1.1 Treamtment

All enrolled subjects will undergo standardized coronary artery bypass grafting (CABG) in accordance with established clinical guidelines. For patients in the cell therapy group, the treatment protocol incorporates myocardial cell transplantation alongside the standard CABG procedure. Following completion of graft anastomoses, a total of 2×10^8 allogeneic human regenerative cardiomyocytes are administered via epicardial injection at 10 sites surrounding the infarcted myocardial region.

Patients in the Cell therapy group were administered the following immunosuppressive regimen: intravenous immunoglobulin (2.5 g, IV) on preoperative day 1, intraoperative day (IOD), and postoperative day (POD) 3, combined with methylprednisolone (500 mg, IV) on preoperative day 1; rituximab (20 mg, IV) on IOD and POD4 to target CD20+ B-cell depletion; oral tacrolimus started preoperative day 3 and dose-adjusted to maintain trough levels within the target range of 3-5 ng/mL, as monitored by blood drug concentration until POD28, concurrently with mycophenolate mofetil (1 g, orally on preoperative day 1, increasing to 1.5 g/day until POD28) and prednisone (20 mg/day started IOD until POD28). The Control group did not receive any immunosuppressive medications. All study subjects

Protocol (version 6.1)

Version data: 2021.08.01

Confidential
Page 19 of 38

undergo intensive postoperative monitoring in the ICU with comprehensive emergency protocols implemented as needed.

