8.4 Post-Transplant Ventricular Arrhythmias Risks and Control

Fatal malignant ventricular arrhythmias constitute a potentially severe risk associated with myocardial cell therapy. Ventricular arrhythmias, particularly polymorphic ventricular tachycardia and ventricular fibrillation, represent significant in-hospital causes of early mortality in myocardial infarction (MI) patients. The resulting tissue architecture, comprising necrotic scar, border zones, and viable myocardium, creates regions of heterogeneous electrophysiology, particularly within the peri-infarct zone, fostering anisotropic conduction and reentrant circuits. Cell therapy targeting the infarcted myocardium inherently modifies this arrhythmogenic substrate. Theoretically, such interventions carry dual potential: therapeutic augmentation of the substrate may reduce arrhythmia susceptibility, while proarrhythmic exacerbation remains a concurrent possibility. Whether cell therapy exerts proarrhythmic effects depends critically upon multiple factors: (1) the specific cell type employed; (2) the degree of electrophysiological integration and coupling between transplanted cells and native myocardium; and (3) intrinsic electrophysiological properties of the transplanted cells themselves. Transplanted cells may introduce novel proarrhythmic substrates by establishing reentrant pathways within scar tissue or inducing arrhythmias via mechanisms of ectopic automaticity or triggered activity.

Animal experimental evidence regarding the proarrhythmic effects of cell-based therapies remains limited and conflicting. Some studies indicate that transplanted cells, which originally lack connexin 43 expression, can acquire this critical gap junction protein postengraftment; connexin 43 is essential for facilitating coordinated electrical conduction within myocardial tissue. However, persistent concerns exist based on studies suggesting that cardiomyocytes derived from embryonic stem cells (ESCs) may harbor intrinsic proarrhythmic risks. Notably, research by Shiba et al. demonstrated that treatment of heart failure in nonhuman primates using induced pluripotent stem cell (iPSC)-derived cardiomyocytes did not result in fatal arrhythmias [18].

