Clinical investigations initiated by [name] et al. (French Academy of Sciences) in 2015, involving multiple patients treated with human pluripotent stem cell (hPSC)-derived cardiac progenitor cells for heart failure [24, 25], have not reported any proarrhythmic effects to date. Nevertheless, further clinical data are required to definitively establish the arrhythmic safety profile of cell-based therapies. Collectively,

Confidential Page 28 of 38

Protocol (version 6.1) Version data: 2021.08.01

current clinical trial results across various cell therapy approaches have not reported significant arrhythmic risks; paradoxically, some evidence suggests stem cell therapy may represent a potential therapeutic strategy for post-infarction ventricular tachycardia. Specifically, transplantation of mesenchymal stem cells into myocardial infarct zones has been associated with myocardial repair, improved cardiac function, and no increased susceptibility to ventricular arrhythmias.

Given the theoretical potential for proarrhythmia associated with allogeneic humanderived regenerated cardiomyocyte therapy in this study, the following risk mitigation measures will be implemented: (1) Continuous electrocardiographic (ECG) monitoring will be employed for all subjects throughout the peri-procedural period. Following hospital discharge, subjects will be provided with remote cardiac monitoring devices at no cost to facilitate ongoing rhythm assessment. This remote monitoring infrastructure enables investigators to promptly evaluate subject cardiac rhythm status and detect potential arrhythmic events in a timely manner; (2) Arrhythmic risk stratification will utilize 24-hour Holter monitoring performed within 24 hours post-procedure; subjects identified as high-risk for ventricular arrhythmias (e.g., frequent premature ventricular contractions [PVCs] >6 per minute) will receive antiarrhythmic prophylaxis.

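### No stated criterion links adverse events in earlier cell-arm subjects to whether the next subject is given the full cell dose

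*Protocol*

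**What the plan says.** All 10 cell-arm subjects are assigned the same dose, 2×10^8 cells at 10 sites (Synopsis; sections 4.1.1 and 6.3). There is no lower dose and no lead-in group. On pace, section 6.2 says: "Patient enrollment is projected to require 6 months".

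Section 6.4 states what precedes each procedure: "Following written informed consent and successful screening, the designated envelope was opened immediately before surgery to reveal group allocation and initiate the assigned procedure".

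Section 8.4 names the main hazard: "Fatal malignant ventricular arrhythmias constitute a potentially severe risk associated with myocardial cell therapy". It adds that "further clinical data are required to definitively establish the arrhythmic safety profile of cell-based therapies". It then announces that "the following risk mitigation measures will be implemented" and lists two. The first is continuous ECG in the peri-procedural period with remote monitoring after discharge. The second is a 24-hour Holter, with antiarrhythmic prophylaxis for a subject found to be at high risk.

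Other safeguards are:
- Section 3: "All patients will undergo rigorous perioperative monitoring (within the first postoperative month) with comprehensive contingency protocols in place".
- Table 3: Holter at D1-D7, D14, D21, M1, M6 and M12.
- Section 9.1: the sponsor confirms that serious adverse events and deaths are reported to the Ethics Committee.
- Section 9.3: the investigator answers for clinical decisions and accepts Ethics Committee supervision.

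The term "Data and Safety Monitoring Board" stands in the List of Abbreviations, and no section shown gives that board a task. Section 6.5.1 describes one analysis, after all subjects have finished.

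**The concern.** The protocol treats fatal ventricular arrhythmia as a recognised hazard of the product and makes sustained VT a primary safety endpoint. It collects the rhythm data that would reveal a problem early. Yet no stated criterion connects what is seen in treated subjects to the decision to inject the next one. Followed as written, the plan would allow all 10 cell-arm subjects to receive the full dose after repeated arrests or sustained VT, with nobody obliged to pause. At stake is the exposure of later subjects to a hazard that earlier subjects had already shown. So is the defensibility of a decision to continue that would have to be improvised after a death in an open-label trial.

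**Working it through.** **Step 1: does any safeguard reach the next subject?**

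| Protocol location | What it triggers | Effect on the next dose |
|---|---|---|
| 6.4, envelope | that subject's consent and screening | none stated |
| 3, contingency protocols | postoperative care of the treated patient | none stated |
| 8.4, ECG and remote monitoring | detection and evaluation | none stated |
| 8.4, Holter | prophylaxis in the same subject | none stated |
| 8.1, new tumor | histopathology of that tumor | none stated |
| 9.1, SAE or death | report to the Ethics Committee | none stated |
| 9.3, Ethics Committee supervision | general oversight | no criterion stated |
| Abbreviations, DSMB | nothing | no role stated |
| 6.5.1, final analysis | after all subjects finish | none |

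**Step 2: pace of dosing.** Six months is 6 × 30.44 = 182.6 days. With even accrual (assumed), cell doses fall 182.6 / 10 = 18.3 days apart. If the first is on day 0, the tenth is on day 9 × 18.3 ≈ 164, before the first cell-arm subject completes six months at about day 183. Only one further cell dose falls before that first subject reaches month 1. Early events can therefore inform most later doses, and late events few.

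**Step 3: what a second-event rule would do.** The protocol gives no event rate or timing, so both are assumed. Simulation: 200,000 trials, 10 cell doses 18 days apart, each subject having an event with probability p at a time uniform in the window shown. Dosing pauses once two events have occurred by 3 days before the next surgery. Cells show P(pause before the tenth dose) / mean number dosed.

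| p | days 0-30 | days 0-180 | days 30-180 |
|---|---|---|---|
| 5% | 0.06 / 9.8 | 0.02 / 10.0 | 0.01 / 10.0 |
| 10% | 0.21 / 9.3 | 0.07 / 9.8 | 0.04 / 9.9 |
| 20% | 0.53 / 7.9 | 0.21 / 9.5 | 0.15 / 9.7 |
| 30% | 0.77 / 6.5 | 0.39 / 8.9 | 0.29 / 9.4 |
| 50% | 0.97 / 4.5 | 0.69 / 7.9 | 0.57 / 8.6 |

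Exact check at p = 0.30: if every event were known at once, P(at least 2 among the first 9) = 1 − 0.7^9 − 9 × 0.3 × 0.7^8 = 1 − 0.040 − 0.156 = 0.804. The simulated 0.77 for early events lies just below this ceiling, as it should.

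The most subjects that could be spared at 30% is 10 − 6.5 = 3.5 (days 0-30) or 10 − 9.4 = 0.6 (days 30-180, close to the primary VT window of months 1-6). Both treat every pause as permanent.

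**Step 4: sensitivity at 30%, same three windows.**
- Check on the day of surgery instead: 0.78, 0.40, 0.31.
- Nine-month enrolment (27-day spacing): 0.79, 0.58, 0.52.
- Only two fixed looks, at day 30 of the third and sixth cell subjects: 0.62, 0.17, 0.09. The running count therefore does most of the work.

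**Step 5: pauses without cell-caused harm.** If the events are background, the same table applies: 1-6% of trials pause at a 5% rate, 4-21% at 10% and 15-53% at 20%, from late to early timing.

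**Step 6: can a check before surgery be carried out as the protocol stands?** Section 4.1.1 has "oral tacrolimus started preoperative day 3", for the cell group only. Section 6.4 reveals allocation immediately before surgery. Read literally, nobody knows three days before surgery who should start tacrolimus. A rule for stopping immunosuppression cannot be written until this is settled.

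**The case against.** The strongest reply is that responsibility is assigned. The investigator is accountable for clinical decisions under Ethics Committee supervision. In a single-centre, open-label trial of 20 with continuous and remote ECG, repeated arrests would be plain to whoever schedules the next operation. The DSMB entry also fits a board whose rules sit in a separate charter, and section 9.2 and the flowchart are not shown. This stands as far as it goes: the protocol does not compel continued dosing, and someone could halt it. But accountability is not a criterion, no text shown refers to a charter, and the contents list titles section 9.2 as concerning the research coordinator. Whether to inject the next subject is trial conduct, which an unseen SAP would not normally govern.

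A second reply is that the benefit rests on assumed rates and shrinks when events come late. That stands. So does the point that a count alone separates a 20% background rate from a 30% rate poorly when events are early (53% against 77% paused), which is why the consequence should be a review.

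A reader might infer that safety surveillance is missing, or that no board exists. The documents support neither: surveillance is substantial, and the text is merely silent on the board's role. Nor does the final analysis in section 6.5.1 rule out safety review along the way.

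**Conclusion.** The point holds as a missing dosing criterion. In the text shown, events in earlier cell-arm subjects have no stated bearing on the next full-dose injection, despite a fatal risk that the protocol itself names and data that it already collects. This finding does not depend on any assumed rate.

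The size of the benefit does depend on them. A reader might take 3.5 subjects spared as the expected gain. It is an upper bound, reached only with a 30% rate, all events in the first 30 days and a pause that is never lifted. With events in days 30-180 the bound is about 0.6 subject. Early events are nevertheless where monitoring is densest: four of the six post-dose Holter time points fall by M1. The change is worth making because it is cheap and protects subjects. Confidence is medium, since a charter may exist unseen.

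**What to change.** Amend sections 3, 6.4 and 9.

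1. **Settle allocation timing first.** Either open the envelope before preoperative day 3, or move the start of tacrolimus, so that sections 4.1.1 and 6.4 agree.
2. **Define the count.** Keep a running total of cell-arm sustained VT/VF, cardiac arrest, and death not clearly explained by CABG or by another identified non-cardiac cause, such as infection under immunosuppression.
3. **Check it** for every subject before preoperative day 3, and again before the envelope is opened.
4. **State the consequence.** At the second event, or another count that the sponsor and board fix beforehand, randomisation and cell dosing pause. Scheduled patients are deferred or receive standard CABG outside randomisation. Once step 1 is settled, add what happens to immunosuppression already begun.
5. **Name who decides.** The DSMB, or the Ethics Committee if there is no board, reviews the events against control-arm counts and decides whether to resume.

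This is a pause for review, with no efficacy test and no alpha spent. Fixed look schedules and staggered dosing are optional. The cost is a protocol amendment and a short charter, with no added visits or procedures, plus the risk of unneeded pauses shown in step 5 of the working, each leading to a review and not a stop.

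### Allocation is revealed just before surgery (section 6.4), but drugs for the cell therapy arm alone start on preoperative day 3 (section 4.1.1), so both cannot be followed

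*Protocol*

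**What the plan says.** Section 6.4 describes sequentially numbered, opaque, sealed envelopes and places the opening after consent and screening: "Following written informed consent and successful screening, the designated envelope was opened". It fixes the moment as well: "the designated envelope was opened immediately before surgery to reveal group allocation and initiate the assigned procedure". From this procedure it concludes: "This ensured allocation concealment during screening and prerandomization phases, preventing selection bias".

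Section 3 makes perioperative immunosuppression part of the cell therapy arm. Section 4.1.1 gives the timing for that arm: "oral tacrolimus started preoperative day 3 and dose-adjusted to maintain trough levels", and on the day before surgery immunoglobulin, "combined with methylprednisolone (500 mg, IV) on preoperative day 1", and "mycophenolate mofetil (1 g, orally on preoperative day 1". For the other arm it says: "The Control group did not receive any immunosuppressive medications".

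Table 3 in section 5.2 has a single pre-surgery column, headed baseline, running from D-14 to D-1. It has no row or visit for randomisation. The six-minute walk test, NYHA class, MLHFQ, PRA and DSA all fall in that column, and section 2.2.2 uses each of them at baseline for a secondary endpoint.

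**The concern.** Drugs that only one arm receives cannot be started before anyone knows which arm the patient is in. Either the envelope is opened earlier than section 6.4 says, or the preoperative doses are not given as section 4.1.1 says. A reader cannot tell when patients were randomised.

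The time of randomisation separates what can depend on the arm from what cannot. If the opening is really on or before D-3, there are some days before surgery in which patient and staff of an open-label, single-centre trial know the allocation. Two things become possible in those days. Baseline measures could be taken with the arm known and, in the cell therapy group only, after immunosuppression has begun. A patient could also withdraw, or surgery be cancelled, for reasons linked to the arm. Either could bias changes from baseline or group comparisons.

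**Working it through.** The protocol states no figure to reproduce here, so the check puts the stated days on one timeline with surgery at D0. I read preoperative day n as D-n. Section 4.1.1 lists the intraoperative day separately, so preoperative day 1 falls before the day of surgery.

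| Event | Stated time | Source |
|---|---|---|
| Baseline window | D-14 to D-1 | Table 3 |
| Tacrolimus starts, cell therapy group only | D-3 | 4.1.1 |
| Immunoglobulin, methylprednisolone and mycophenolate start, cell therapy group only | D-1 | 4.1.1 |
| Envelope opened | D0, just before surgery | 6.4 |

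**Step 1, the gap.** From D-3 to D0 is 3 days. Drugs specific to one arm that are due before the opening: 1 (tacrolimus) + 3 (the others) = 4. A generous reading of section 6.4, with the opening on D-1, still leaves tacrolimus 3 − 1 = 2 days too early.

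**Step 2, can any course of action satisfy both sections?**
- Open at D0: the preoperative doses cannot be directed to the cell therapy group alone.
- Treat everyone before surgery: the control group is then exposed, against section 4.1.1.
- Open by D-3: the preoperative doses can be given, but section 6.4 is not followed.

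None satisfies both.

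**Step 3, overlap with baseline if the opening is by D-3.** The window D-14 to D-1 has 14 days. Preoperative dosing covers D-3 to D-1, which is 3 days. That leaves 14 − 3 = 11 days (D-14 to D-4) free of study drug. Every baseline test could be finished in those 11 days, but nothing in Table 3 requires it.

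**Step 4, which baseline measures are exposed.** Section 6.4 opens the envelope only after screening is passed, so values that decide eligibility must already exist. That covers NYHA class (inclusion 4), PRA and DSA (exclusion 1), and haematocrit, white cells and platelets (exclusion 9). The walk test and MLHFQ are not eligibility criteria, so nothing ties them to a time before opening.

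**Step 5, scale of preoperative loss.** With 10 patients per arm, one patient is 1/10 = 10% of an arm. This is only a unit of scale: the protocol gives no rate of withdrawal before surgery.

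**The case against.** The strongest reply accepts the timing clash and disputes what follows from it. Several of its points stand.

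- **Concealment.** A reader might infer that allocation concealment has failed and that selection bias is present. The document does not support that. Sealed, opaque, numbered envelopes opened at D-3, after consent and completed screening, would still hide the allocation up to enrolment. What fails is the stated moment of opening. Arm-dependent withdrawal after opening is loss after randomisation, a different problem from the selection bias that section 6.4 addresses.
- **Baseline.** A reader might infer that changes from baseline are biased. The overlap is permitted, not forced, and nothing shows that any assessment falls in D-3 to D-1.
- **Which measures.** NYHA class, PRA, DSA and blood count are poor examples, because passing screening requires them before opening. Table 3 also schedules blood count at baseline only, and the cytokine panel is not a named endpoint.
- **Mitigation.** Section 6.4 blinds the efficacy assessors. Both primary endpoints are postoperative incidences that do not use the baseline walk test or MLHFQ. Assessor blinding does not, however, blind the patient, and those two measures rest on patient effort and self-report.
- **What is unknown.** The document does not show which section is followed in practice, and the flowchart in section 5.1 is not readable in the copy reviewed. An earlier allocation step shown there would still conflict with the text of section 6.4.

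None of this removes the contradiction between sections 6.4 and 4.1.1.

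**Conclusion.** The point holds as an internal contradiction. The randomisation timing in section 6.4 and the preoperative dosing of one arm in section 4.1.1 cannot both be carried out, and this applies to all 10 planned cell therapy patients. The gap is 3 days, or 2 if section 6.4 is read as allowing the day before surgery.

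The consequences are conditional. If allocation is known by D-3, 3 of the 14 baseline days fall after allocation and, in one arm, on drug. Baseline measures not needed for eligibility could be affected, and arm-dependent loss before surgery becomes possible. The protocol gives no basis for putting a size on either effect.

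The conclusion rests on reading preoperative day n as D-n and on there being no earlier allocation step in the unreadable flowchart. The first assumption affects only the exact number of days, because the preoperative doses precede the day of surgery in any case. Which patients are counted in which analysis may be set in a statistical analysis plan that is not shown, so its absence here is not part of this point.

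**What to change.** Reconcile sections 6.4, 4.1.1 and 5.2:

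1. In section 6.4, state that the envelope is opened after consent, confirmed eligibility and completion of all baseline assessments, and before the first allocation-dependent dose, with the date and time of opening recorded.
2. In Table 3, add a randomisation row and a footnote closing the baseline window at envelope opening in both arms.

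This is a few sentences and a table entry. The practical cost is that baseline tests must finish a few days earlier, and some patients may be lost between opening and surgery, after they have been randomised. The drug schedule itself is not judged, and no change to it is proposed.
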